#### 1. BACKGROUND AND SIGNIFICANCE

Alzheimer's Disease (AD)is a looming epidemic, with an urgent need for new therapies to delay or prevent symptom onset and progression. There is growing awareness that clinical trials must target stage-appropriate pathophysiological mechanisms to effectively develop disease-modifying treatments.1 Advances in AD biomarker research have demonstrated changes in amyloid, brain metabolism, and other pathophysiologies prior to the onset of memory loss, with some markers possibly changing one or two decades earlier . The brain region responsible for spatial navigation and memories of experience, the hippocampus, is one of the areas first affected in Alzheimer's disease (AD) and other memory disorders. 4,5 Researchby [name] has shown how coordinated electrical activity across many neurons in the hippocampus represents memories of experiences and this coordinated activity fails in animal models of AD. The work also showed that stimulating neurons to produce a specific component of this activity, called gamma oscillations, reduces AD pathology. The goal of this proposal is to translate our discovery that stimulating specific patterns of neural activity is neuroprotective from rodents to humans using a non-invasive approach. This first study will establish the feasibility and tolerability of using this non-invasive method to drive gamma in humans. This research includes preclinical testing that will be used to design and justify a multi-site clinical trial to test this approach as a treatment for AD, for which there are currently no effective therapies.

**Preclinical studies** by [name] and collaborators recently reported a powerful new discovery in *Nature*: driving specific patterns of neural activity recruits the brain's immune system and reduces AD pathology.In AD mice, deficits were found in 20-50Hz electrical neural activity that has long been linked to memory, attention, and perception, called gamma oscillations. Deficits in gamma oscillations occurred in presymptomatic mice, suggesting that they may contribute to early disease progression. Surprisingly, stimulating neurons to produce gamma oscillations ("drive gamma") mobilized the immune system to remove

amyloid beta, a protein whose aggregation is thought to initiate neurotoxic events. Specifically, driving gamma recruited the primary immune cells of the brain, microglia, to increase engulfment of beta amyloid, resulting in 40% reduction in beta amyloid (Fig. 1).

[figure not shown]

Figure 1: Stimulating brain circuits to produce gamma oscillations (left) reduces amyloid beta levels (center) and recruits microglia to take up amyloid (right).

In the animal studies, invasive to take up amyloid (right).
optogenetics (which requires virus infection and fiber implants to drive neural activity with light) were used to drive gamma.

To translate this discovery to humans, [name] and colleagues developed a method to drive gamma non-invasively: flickering lights at gamma frequency, like a strobe light but faster, to drive gamma oscillations in visual brain areas (Fig. 1). This simple non-invasive manipulation can be applied to humans to determine if this approach can be used therapeutically.

Blood flow through the brain is crucial for neural function and clearance of pathogens.Blood flow decreases very early in Alzheimer's disease and this decrease is thought to lead to amyloid build up and functional deficits.In preliminary studies, driving gamma leads to dilation of blood vessels even after manipulation of activity ceases. One hour after gamma light flicker ends, the diameter of small blood vessels is increased by 33% and pathogenic

proteins appear co-localized with these vessels (Fig. 2). We hypothesize that this dilation of blood vessels contributes to the decrease in pathogenic proteins following gamma light flicker by increasing clearance via the blood steam. Accordingly, we will assess the effects of driving gamma on blood flow to reveal an entirely new effect of stimulating gamma oscillations. Stimulating activity to increase blood flow may reduce pathogenic proteins and could have broad implications for brain health.

[figure not shown]

Figure 2: Gamma light flicker for 1 hour increases blood vessel diameter in visual cortex and hippocampus relative to dark controls.

Clinical and preclinical studies have demonstrated that gamma activity can be increased via exposure to several different types of sensory stimuli. Recent preclinical findings published in *Nature* have demonstrated that this increase in gamma activity both reduced the production of beta-amyloid plaques and increased the rate of clearance in the brains of mice. Preliminary (unpublished) data using combined audio and visual sensory stimulation has demonstrated improvement in cognitive behavioral tasks in preclinical mouse models of AD following this intervention. Non-invasive sensory stimulation paradigms thus hold therapeutic promise for those individuals with mild cognitive impairment, Alzheimer's disease or related disorders.

The specific modalities have been chosen because they have been widely used in previous clinical research for a variety of goals, including the characterization and understanding of gamma brain activity in younger and older adults. For example, the most efficient forms of visual stimulation for generating gamma activity (including properties such as frequency and intensity) have been identified. For auditory stimulation, the test-retest reliability of its effect on gamma brainwave activity is high and the gamma response induced by auditory "click-train" stimuli at 30-50 Hz has been proposed as a quantitative measure of hearing loss in old age, an indicator for neurodevelopment conditions such as schizophrenia and neurodegenerative conditions such as Alzheimer's disease.

The urgent and essential next step of this work is to translate these discoveries to humans in a clinical investigation. This pilot study in humans will focus on feasibility and safety. Our central hypothesis is that driving gamma via sensory flicker will be feasible and tolerable. Our secondary hypothesis is driving gamma alters the brain's immune cells and amyloid beta processing. The primary outcomes will be feasibility and tolerability. Exploratory measures will include amyloid and immune signals in the CSF and brain and alterations in cerebral blood flow, as seen through arterial spin-labeling (ASL) magnetic resonance imaging (MRI).

## 2. SPECIFIC AIMS

- **2.1**Aim 1. Assess the safety, and tolerability of gamma flicker and subject compliance. We will determine in 10 subjects with a diagnosis of MCI whether flicker exposure for 1 hour every day is well tolerated and whether subjects comply with the study procedures. In addition, we will closely monitor the safety of this procedure and document the occurrence of any adverse events.
- **2.2**Aim 2. Assess effects of driving gamma on blood flow in patients with MCI. Blood flow decreases very early in Alzheimer's disease and this decrease is thought to lead to amyloid build up and functional deficits. We will determine if gamma flicker increases blood flow in Alzheimer's patients. We will perform these tests in approximately 10 patients with mild cognitive impairment (MCI) in collaboration with Dr.'s [name] and [name] and the Emory BHC/ADRC. These pilot studies will support our application for an NIH grant to test gamma flicker in Alzheimer's patients in a clinical trial.
- 2.3 Aim 3. Assess effects of driving gamma on amyloid beta levels and inflammation markers in patients with MCI. We will assess amyloid beta levels in the brain (florbetapir PET), cerebral spinal fluid (Aß42 Luminex assay), the current gold standards in the field, and in the retina (Neurovision), a new approach currently being validated at the Emory Brain Health Center. We will also assess inflammatory markers in the cerebral spinal fluid (OLink inflammatory panel). We will perform these tests in 10 patients with mild cognitive impairment (MCI), as determined by clinical or research assessment using local standards at the Emory Brain Health Center (BHC)/ Alzheimer's Disease Research Center (ADRC).

#### 3. PRELIMINARY DATA

**3.1** *Current work in humans*— Cognito Therapeutics has licensed the technology from MIT to transition this work to humans. The company will provide the flicker devices for

conducting the study here at Emory. The device is similar to sunglasses and is both comfortable and easy to use (Figure 3, *redacted*).

Initial human studies of patients with cognitive impairments have demonstrated that sensory stimulation can be safely delivered and is well-tolerated. Three clinical studies have been sponsored by Cognito Therapeutics, which have been conducted under IRB approval (non-significant risk designation) and with good clinical practice (GCP) using a combination of non-invasive sensory stimulation systems in patients with cognitive impairments. These studies used three sensory stimulation modalities: visual, auditory, and tactile. For the visual and auditory stimulation, the Visual Flicker Unit (COG-VSU001) and Auditory Click Unit (COG-ASU001) were utilized, which have similar output light intensity, sound volume, repetition rate (40 cycles/second), and duty cycle to the Gamma Sense Stimulation System that will be used for this study. For the tactile stimulation, transcutaneous electrical nerve stimulation (TENS) was delivered to the palm of the hand using the Peripheral Nerve Stimulation Unit (COG-NSU001). Tactile stimulation is not included in the clinical investigation described by this protocol.

redacted

## 4. EXPERIMENTAL DESIGN AND METHODS

4.1 Overview: For this 9-week study, 10 subjects with mild cognitive impairment (amnestic or multi-domain subtypes) will be randomly assigned to two study arms. Although all participants will receive Flicker exposure, half of the participants will receive the exposure (driving gamma) during the entire study period (8 weeks of Flicker) while the other half of the participants will receive Flicker exposure for half of the study period (2nd 4-weeks). During the 9-week course of the study, participants will undergo venous blood draws and lumbar puncture for biomarker analyses at baseline, midpoint and at 9 weeks. At the study week 4 time point, the participants currently undergoing Flicker exposure will continue with their sessions while at week 4, those initially randomized to non-exposure will initiate Flicker exposure. The primary goals are to measure safety and FLICKER tolerance while verifying the intended response. Secondary objectives include monitoring possible effects of Flicker exposure on clinical findings and biomarkers of AD progression, including CSF amyloid, tau, and phospho-tau, and volumetric MRI, as well as PET (florbetapir) and arterial spin labeling MRI and retinal amyloid changes.

**4.2 Sample Size and Power.** This is a pilot study designed to assess feasibility and tolerability in the patient population. Although the sample size of 10 subjects will allow us to make certain claims about tolerability, we do not anticipate generating clinically meaningful,

broadly applicable results from this data. Thus, our sample size is driven by the need to collect pilot data that will position us to develop a clinical trial, if warranted, based on the technology described here.

- **4.3 Flicker tolerance to date.** For studies conducted to date by Cognito Therapeutics, a total of 17 participants have undergone daily periods of sensory stimulation for up to one hour (the study paradigm planned for this work). These subjects include young adults, older adults, and older adults with cognitive impairments. These studies have helped establish the feasibility of sensory stimulation with regards to safety, comfort, and tolerability of the exposure in patients with mild-to-moderate cognitive impairments. No device or exposure-related adverse events have been reported during this study.
- **4.4 Future research samples.** Per participant consent, blood, cell lines and cerebrospinal fluid samples will be stored indefinitely and may be used for future investigation, potential development of new biomarkers, and potential treatments for Alzheimer's disease. Samples may also be used to deal with future safety issues for Mild Cognitive Impairment or Alzheimer's disease that are not presently known. These stored samples may also be used for genetic (DNA) research.

#### 6. SAFETY MONITORING AND ADVERSE EVENT REPORTING

**6.1 Internal Safety Monitoring** Subjects will be monitored remotely to determine whether they are performing the proper Flicker exposure at home. The study coordinator will call 1 time during week 1 of the exposure phase to check on the participants. During the first week, the study coordinator will also visit the participant at home to observe the session. During weeks 2 – 4 of the study, the study coordinator will check-in with participants weekly by telephone. Subjects in the Non-exposure/Flicker group will be monitored in the same manner throughout their 4 weeks of Flicker exposure.

Internal monitoring will be performed by the Investigators who will review data from the study visits and review all aspects of patient safety. Serious and unexpected adverse events and/or unanticipated problems involving risks to participants or others will be reviewed and reported to the Emory IRB, as per the Emory IRB policies and procedures, by the research coordinator in collaboration with the investigators.

**6.2 Emory University Investigational Review Board (IRB)** policies and procedures will be employed:

Unanticipated Problems involving Risks to Participants or Others (UPs): The PI will report to the IRB (using any IRB specified forms, as applicable) any UP in accordance with the timetable set forth in the provision below entitled Timetable for Reporting. The PI will advise the Emory IRB of: (a) the relationship between the problem and the intervention or study protocol; (b) whether or not a protocol change is necessary to reduce risk; and (c) whether the information about the problem affects the informed consent process.

**Serious Adverse Events:** At the time of renewal for the study, the PI will report to the Emory IRB a summary of the serious adverse events related to the research that occurred in the previous approval period. If adverse events occur at a greater frequency, severity, or duration than was previously anticipated, those become unanticipated and are promptly reportable.

**Protocol Deviations:** The PI will report to the Emory IRB any circumstances of which the PI becomes aware per which there has been a substantive deviation from the protocol that adversely affected at least one of the following: 1) the rights, welfare, or safety of subjects; 2) the subjects' willingness to continue participation; or 3) the integrity of the research data. Deviations that are reported as protocol modifications undertaken to eliminate apparent immediate hazards to Human Subjects do not need to be reported twice. The IRB will evaluate reported protocol deviations to determine any action to be taken or other reporting requirements that need to be fulfilled.

**Protocol Modifications:** The PI will request approval of any changes (including, but not limited to, any changes in research personnel) that the PI plans to make to a Research protocol, which has already been approved by the Emory IRB. Except in cases in which the change must be made to eliminate apparent immediate hazards to Human Subjects, the Emory IRB must approve of the modification **before** it can be initiated.

Protocol: v07

**Non-Compliance:** The PI shall notify the IRB of any circumstances of which the PI becomes aware of failure to follow Emory IRB Policies &Procedures, federal regulations, or other applicable laws. This report shall be made to the IRB as soon as possible after the non-compliance occurs. The IRB will work closely with the PI to develop a reasonable corrective and preventive action plan that can be implemented by the study team.

#### 7. PATIENT SELECTION

**7.1 Recruitment Plan.** The Emory ADRC has a large clinical practice and clinical research registry of subjects interested in participating in research studies. As of December 2017, the ADRC registry has an enrollment of 447 participants, among them 110 with MCI. The MCI participants include 100 individuals with amnestic MCI (single or multiple domain). These ADRC participants have annual research evaluations that include detailed cognitive assessments, and all have consented to be contacted for opportunities to participate in research studies. In addition to the existing pool of ADRC participants, the Emory memory disorders clinics, staffed by Drs. [name], [name], and other specialty-trained health professionals provide evaluation and treatment ~2000 patients annually, of whom ~500 are new visits (and ~100 MCI). Potential study subjects will be identified from those subjects being followed by the Emory Alzheimer's Disease Research Center and by the patients of the PIs. Other potential study subjects may be recruited if they contact the Emory ADRC specifically to find out about potential research studies that might be appropriate for either themselves or a family member.

#### 7.2 Inclusion Criteria

- 1. Subjects must have a subjective memory concern as reported by subject, study partner or clinician.
- 2. Meets local criteria for diagnosis of MCI. Subjects with amnestic (single or multi-domain) will be eligible, as both subtypes of aMCI are at high risk for progression to AD
- 3. Montreal Cognitive Assessment (MoCA)score ≥15. Exceptions may be made for subjects with less than 8 years of education at the discretion of the PI.
- 4. Clinical Dementia Rating = 0.5. Memory Box score must be at least 0.5.
- 5. General cognition and functional performance sufficiently preserved such that a diagnosis of AD cannot be made by the physician at the time of the screening visit.
- 6. Stable on medications for 4 weeks prior to initiation of study sessions.
- 7. Geriatric Depression Scale (GDS) ≤ than 6.
- 8. Male or female outpatients aged 50-90 (inclusive).
- 9. Able to hear without the use of hearing aids.
- 10. Study partner who lives with the participant and can provide a reliable assessment of the participant's level of function, is available for all clinic visits, and can serve as a supervisor/monitor for the home-based Flicker sessions for the duration of the study.
- 11. Visual and auditory acuity adequate for neuropsychological testing.
- 12. Good general health with no diseases expected to interfere with the study.
- 13. Completed six grades of education or has a good work history (sufficient to exclude mental retardation).

- 14. Able to communicate in English with study personnel.
- 15. Able to understand the nature of the study and provision of written informed consent prior to conduct of any study procedures.
- 16. Willing to undergo repeated MRIs and PET scans. No medical contraindications to MRI.
- 17. Agrees to blood collection for APOE and biomarker testing.
- 18. Agrees to lumbar puncture over the course of the study for the collection of CSF.CSF levels of Ab42, total Tau, and Tau phosphorylated at threonine 181 consistent with underlying AD pathology according to established threshold values at Emory.

#### 7.3 Exclusion criteria

- Any significant neurologic disease other than MCI and suspected incipient AD, such as Parkinson's disease, multi-infarct dementia, Huntington's disease, normal pressure hydrocephalus, brain tumor, progressive supranuclear palsy, poorly controlled seizure disorder, subdural hematoma, multiple sclerosis, or history of significant head trauma followed by persistent neurologic deficits or known structural brain abnormalities.
- 2. Screening/baseline MRI scan with evidence of infection, large vessel infarction or other focal structural lesions that could account for the memory deficits. Subjects with multiple lacunes or lacunes in a critical memory structure are excluded.
- 3. Contraindication to MRI due to pacemakers, aneurysm clips, artificial heart valves, ear implants, metal fragments or foreign objects in the eyes, skin or body, or excessive weight.
- 4. Presence of clinically significant suicide risk based on the Investigator's judgment informed by a structured clinician interview. Any suicide attempt within the past 1 year of the screening visit is exclusionary.
- 5. Major depression, bipolar disorder as described in DSM-IV within the past 1 year, or history of schizophrenia (DSM-IV). Psychotic features, agitation or behavioral problems within the last 3 months which could lead to difficulty complying with the protocol.
- 6. History of alcohol or substance abuse or dependence within the past 2 years (DSM-IV criteria).
- 7. Known history of epilepsy or migraines, which may be exacerbated by study intervention.
- 8. History of narrow angle (acute angle) glaucoma.
- 9. Current use of warfarin or other blood thinners (exclusionary for lumbar puncture).
- 10. Inability to obtain initial CSF sample.
- 11. Current use of Namenda (memantine).
- 12. Current use of medications that lower seizure threshold, including Wellbutrin, Ciprofloxacin, Levofloxacin, Seroquel, Phenergan, and Sumatriptan.
- 13. Current use of anti-psychotic medication.
- 14. CSF profile inconsistent with underlying Alzheimer's Disease pathology.
- 15. Reasonable likelihood for non-compliance with the protocol or any other reason, in the opinion of the investigator, prohibits enrollment of subject into the study.

16. Exceptions to these guidelines may be considered on a case-by-case basis at the discretion of the protocol director.

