#### **Baseline Visit 2b:**

- Interim history review
- Medication review
- Adverse event review
- Confirm continued eligibility
- Vital signs, height & weight
- Physical and neurologic exams
- Cognitive testing/Questionnaires
  - Category Fluency (Animals)
  - o Benson
  - Trails A & B
  - Boston Naming Test (30 item)
  - Clinical Dementia Rating (CDR)
  - Neuropsychiatric Inventory (NPI)
  - Activities of Daily Living (FAQ)
- EEG
  - Flicker entrainment with exposure titration
  - EEG evaluation and induced activity
- Eye tracking task
- Randomization
  - Assigned to Flicker for 1st 4-weeks or 2nd 4-weeks
- Instructions for at-home Flicker sessions
  - Daily journal

**8.4 Study Visits.** Study visits at Emory may take place on more than 1 day to accommodate all the scheduled procedures (e.g., Visit 1 may be 2 days)

**Week 1** (Flicker administration [will start in study week 4 for half of participants and procedures will be identical to those followed for the Flicker/Flicker group])

- Days 1 -7
  - In-home therapy
  - Telephone call/email contact
    - Assessment of adverse events

- Answer any questions
- Remote adherence monitoring
  - If session has not been completed by 2:00 pm, reminder call is placed
- Day 3, 4 or 5
  - In-home Observation visit

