#### **Weeks 2 – 4**(Days 15 - 28)

- In-home therapy
- Telephone call/email contact
  - Assessment of adverse events
  - Answer any questions
- Remote adherence monitoring
  - If session has not been completed by 2:00 pm, reminder call is placed
- Flicker administration will continue until all assessments have been completed.

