#### 8.6.2 Other Assessments:

- a. Demographic Data Demographic data (gender, date of birth, marital status, ethnicity, race) will be collected for all patients.
- b. Concomitant Medication All meds taken by subjects as part of their routine health care will be documented during the study.

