## 8.8 Schedule of Assessments

On the following pages, the schedule of assessments for both treatment groups is presented.

Table 1. Schedule of Assessments for the Non-Exposure Phase/Flicker Exposure Phase

Visit Number	1a	1b	2a	2b	3	4	5	6a 	6b	7	8	9	10	11a 	11b
Study Week	Screening 		Baseline 		1	2	3	44	44	5	6	7	8	94	94
Consent	X														
Confirm eligibility	X			X											
Medical history and medication review	X							X						X	
Physical exam and neurological exam	X			X				X						X	
Vital signs + height + weight	X			X											
Sensory function (see/hear)	X							X							
APOE genotyping		X													
Blood for biomarkers		X							X						X
Cognitive assessments	X			X				X						X	
Retinal imaging		X							X						X
MR imaging	$X^5$		$X^5$					$X^3$	$X^3$					X	
Lumbar puncture		X							X						X
PET Scan			X					X						X	
Eye tracking				X				X						X	
EEG evaluation and induced activity	$X^6$			X				X						X	
Tolerance Testing	X							X						X	
Randomization/Study crossover				X				X							
Therapy training									X						
In-home observation visit										X					
In-home therapy										X	X	X	X		
Telephone call / email contact					X	X	X			X	X	X	X		X
Remote adherence monitoring										X	X	X	X		
Assessment of adverse events				X	X	X	X	X		X	X	X	X	X	

<sup>1Crossover visit (2-day visit) End of treatment visit (2-day visit)

<sup>3MRI will occur on either study visit 6a or 6b

<sup>4Study visits may extend over several days, depending on scheduling constraints

<sup>5MRI will be done at visit 1a if not done within the past 2 yrs or at 2a if done within the past 6 months

<sup>6Screening EEG may be repeated if entrainment criteria are not met or data are unreliable in subjects who have met all other eligibility criteria.

Table 2. Schedule of Assessments for the Flicker Exposure/Flicker Exposure Phase

Visit Number	la .	1b	2a	2b	3	4	5	6	7a 	7b	8	9	10	$11a^2$	11b
Study Week	Screening 		Baseline 		1	2	3	4	5 	5 	6	7	8	94	94
Consent	X														
Confirm eligibility	X			X											
Medical history and medication review	X								X					X	
Physical exam and neurological exam	X			X					X					X	
Vital signs + height + weight	X			X											
Sensory function (see/hear)	X								X						
APOE genotyping		X													

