Blood for biomarkers		X								X					X
Cognitive assessments	X			X					X					X	
Retinal imaging		X								X					X
MR imaging	X 		X 						$X^3$	$X^3$				X	
Lumbar puncture		X								X					X
PET Scan			X						X					X	
Eye tracking				X					X					X	
EEG evaluation and induced activity	$X^6$			X					X					X	
Tolerance testing	X			X					X					X	
Randomization				X											
Therapy training				X											
In-home observation visit					X										
In-home therapy					X	X	X	X	X	X	X	X	X		X
Telephone call / email contact					X	X	X	X			X	X	X		
Remote adherence monitoring					X	X	X	X	X	X	X	X	X		
Assessment of adverse events				X	X	X	X	X	X		X	X	X	X	

<sup>1Midpoint clinic visit (2-day visit)

<sup>2End of treatment visit (2-day visit)

<sup>3MRI will occur on either study visit 7a or 7b

<sup>4Study visits may extend over several days, depending on scheduling constraints

<sup>5MRI will be done at visit 1a if not done within the past 2 yrs or at 2a if done within the past 6 months

<sup>6Screening EEG may be repeated if entrainment criteria are not met or data are unreliable in subjects who have met all other eligibility criteria.

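### The main-phase calls ask about adverse events but not medication, so a new seizure-threshold-lowering drug could run alongside daily flicker for about 4 to 5 weeks before any scheduled question

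*Combined protocol and SAP*

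**What the plan says.** Exclusion 12 in section 7.3 is an entry criterion: "Current use of medications that lower seizure threshold, including Wellbutrin, Ciprofloxacin, Levofloxacin, Seroquel, Phenergan, and Sumatriptan". Exclusion 7, on epilepsy and migraine, reflects the same worry about what the intervention might provoke. The text available for review states no on-study ban on these drugs.

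During home flicker, section 6.1 provides one call and one home visit in the first week; after that "the study coordinator will check-in with participants weekly by telephone". The delayed arm is followed in the same way once its flicker begins. Section 8.4 gives the content of these contacts: "Assessment of adverse events" and answering questions. Neither section adds a medication item.

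In 8.8, the row "Medical history and medication review" is marked at 1a, 6a and 11a in Table 1, and at 1a, 7a and 11a in Table 2. The text of 8.3 also lists it at Baseline Visit 2b. No visit marked "Telephone call / email contact" during flicker carries it. In the extension (section 11 and Table 3), all three calls (Visits 12, 14 and 16) include medication.

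Section 8.6.2 makes a general commitment: "All meds taken by subjects as part of their routine health care will be documented during the study". It does not say when or at which contact. Inclusion 10 requires a co-resident study partner who "can serve as a supervisor/monitor for the home-based Flicker sessions for the duration of the study".

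**The concern.** The protocol treats a lowered seizure threshold as reason enough to keep someone out, yet has no scheduled way to learn promptly that a participant has since started such a drug. Participants are outpatients aged 50 to 90 taking an hour of flicker a day at home, and other clinicians may prescribe for them.

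Two things are at stake. The first is safety: the investigator can weigh a new drug against continued flicker only after hearing of it. The second is interpretation: safety and tolerability are Aim 1, in 10 participants, and an adverse event reported by telephone is easier to attribute with a recent medication history beside it. Staff may ask after an event, but the plan does not schedule the question.

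The point is limited to timing. It does not claim a breach of exclusion 12, or that new drugs would never come to light.

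**Working it through.** The plan states no figure for this interval, so there is none to reproduce. The check counts days between scheduled medication questions and converts them to expected drug days.

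**Calls during flicker that carry a medication mark**

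| Schedule | Calls | Marked |
|---|---|---|
| Table 1 (delayed arm) | visits 7, 8, 9, 10 | 0 of 4 |
| Table 2 (Flicker/Flicker) | visits 3, 4, 5, 6, 8, 9, 10 | 0 of 7 |
| Table 3 (extension) | visits 12, 14, 16 | 3 of 3 |

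**Interval G between scheduled medication questions**

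Week w is taken as days 7(w − 1) + 1 to 7w.

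- Flicker/Flicker, start of flicker to 7a in week 5: 28 days nominal, 28–34 depending on the visit day.
- Flicker/Flicker, 7a in week 5 to 11a in week 9: 7 × (9 − 5) = 28 days nominal, range 22–34.
- Delayed arm, 6a in week 4 to 11a in week 9: 7 × (9 − 4) = 35 days nominal, range 29–41.
- With a medication question at every weekly call: 7 days nominal, at most about 13 if one call falls early in its week and the next falls late.

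In the delayed arm, how many of the 35 days are on flicker depends on when it starts. Table 1 first marks home therapy in week 5, which gives 28 days. Section 8.4 says flicker "will start in study week 4 for half of participants", which gives up to 35.

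**Drug days before the first scheduled question**

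Assume a course of L days starts at a time uniform over an interval of G days. The mean number of drug days before the next question is

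- L − L²/(2G) if L ≤ G
- G/2 if L > G

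For example, with L = 14: 14 − 196/56 = 10.5 for G = 28, and 14 − 196/70 = 11.2 for G = 35. With G = 7 the course outlasts the interval, so the mean is 7/2 = 3.5.

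| Course | G = 28 | G = 35 | G = 7 |
|---|---|---|---|
| 5 days | 4.55 | 4.64 | 3.21 |
| 7 days | 6.12 | 6.30 | 3.50 |
| 14 days | 10.5 | 11.2 | 3.5 |
| Continuing | 14 | 17.5 | 3.5 |

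Even with weekly questions, (7 − 5)/7 = 29% of 5-day courses would end before the next call.

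**Exposure and workload**, assuming 5 participants per arm: flicker 5 × 8 + 5 × 4 = 60 participant-weeks; calls during flicker 5 × 7 + 5 × 4 = 55.

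**The case against.** The strongest reply accepts the facts and disputes their weight.

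- *The extension is no model for timing.* Its legible contacts fall at weeks 24, 36 and 48, so medication questions are about 84 days apart while flicker continues. By the same formula a continuing drug would run a mean of 42 days unasked. This stands: Table 3 shows only that the question suits a telephone call, not that 4 to 5 weeks is too long. The longer extension interval does not close the main-phase one.
- *Exclusion 12 is not absolute.* Exclusion 16 allows case-by-case exceptions, and no on-study ban is stated. True, but a case-by-case judgement needs someone to know about the drug.
- *Other routes exist.* The adverse event question, the first-week home visit, the study partner or the daily journal might reveal a drug. They might, but none is a scheduled medication question, and the journal's content is not described. Continued eligibility is confirmed only at clinic visits, so it leaves the same interval.
- *Blank table cells are weak evidence.* The tables also leave vital signs unmarked at midpoint and end of study, where 8.4 lists them. This is fair. The finding rests as much on the contact content in 8.4 and on 6.1, which agree with the tables here.
- *Days to a question are not a risk.* Correct. No incidence of new drugs and no seizure rate is given, and section 4.3 reports no device- or exposure-related adverse events in 17 earlier participants, too few to exclude a risk.
- *Unseen text.* The part of the protocol between 4.4 and section 6 was not available, so an on-study medication rule there cannot be excluded.

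**Conclusion.** The concern holds. Followed as written, the main phase leaves a nominal 28 to 35 days between scheduled medication questions, at least 28 of them on daily flicker. Asking at each call cuts this to about 7 days.

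The gain is large for courses of two weeks or more and small for short ones: about 1.3 to 1.4 days on average for a 5-day course. These means assume a uniform start within the interval and evenly spaced calls. They measure delay in notice, not probability of harm. With unknown incidence and about 60 participant-weeks, the number of cases could be zero. This is an inexpensive safety improvement that should be made; it is not a flaw that undermines the trial.

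**What to change.** In 6.1, and under each telephone or email contact in 8.4, add an item such as *new or changed medication since the last contact*, asked of both participant and study partner. Mark medication review in the call columns during flicker: visits 7–10 in Table 1, and visits 3–6 and 8–10 in Table 2.

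State that any drug of the kind in exclusion 12 is referred to the investigator; what follows is for the investigator and sponsor. Exclusion 13 (antipsychotics) is also worded as current use and could be referred the same way, although the seizure argument here concerns item 12. As a purely clerical matter, mark medication review at 2b in both tables to agree with 8.3.

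The cost is one extra question in about 55 calls already planned, with no added visit, staff or equipment. It brings detection forward but does not prevent all co-exposure.
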